3.9. EXPLORATORY ENDPOINT

- IgA antibodies against PT, FHA, PRN, and fimbriae 2/3 in nasopharyngeal aspirate at visits 2, 4, 6, 7, 8, 9 and 10
 - Geometric mean levels
 - Number and proportion of participants with positive responses, defined by at least 100% increase from pre- to post-vaccination, to at least 4 times MLD after vaccination.
- Cytokine levels in nasopharyngeal aspirate (exploratory assay)
 - Median + IQR of concentration and fluorescence intensity per cytokine, assessed by Luminex pre and post vaccination
- Cytokine levels in cell culture supernatants after stimulation of PBMC with PT, FHA, PRN and unrelated antigen
 - Median + IQR of concentration and fluorescence intensity per cytokine, assessed by Luminex in PBMC supernatant after stimulation pre and post vaccination
- Median number of spot-forming units determined by ELISpot/FluoroSpot assay of pertussis-specific cytokine-positive T-cells after stimulation of PBMC with PT, FHA, PRN and unrelated antigens.
- Median number of spot-forming units determined by ELISpot assay of pertussis-specific IgG-producing memory B-cells after stimulation of PBMC with PT, FHA, PRN and unrelated antigens.

Intra-group comparisons compared to baseline will be done by statistical tests for paired samples. Multiplicity adjustments methods based on the FDR may be considered for the analysis of high dimensional immunogenicity assays (Luminex assays; assays on PBMC with various stimulation conditions).

In addition, in ancillary analyses, appropriate statistical models for the analysis of longitudinal data may be used to estimate the slopes of changes in immunogenicity markers per group. Methods for high-dimensional data may be used to assess the interrelationships between different immunogenicity markers.

3.10. INTERIM REPORTS FOR DSMB

Overall, per group and randomized allocation, and by period (pre/post vaccination):

- Number and proportion of participants with at least :
 - one AEFI during available follow-up
 - one AR during available follow-up
 - one SAE during available follow-up
 - one work accident
- Number of following AEs during available follow-up:
 - Solicited or unsolicited adverse reaction from respiratory tract
 - AEFI with difficulties in breathing (asthma, spasmodic cough, pneumonia)
 - Cough
 - spasmodic cough
 - solicited systemic adverse event
 - unsolicited adverse event

- Participants with at least one cough or spasmodic cough of grade 2 or higher between Day 0 and Day 28 (n, %)
- Participants with at least one other respiratory tract AE related or possibly related to vaccination of grade 3 or higher between Day 0 and Day 28 (n, %)
- Participants with any other AE related or possibly related to vaccination of grade 3 or higher between Day 0 and Day 28 (n, %)
- Participants with at least of the adverse events listed above (primary endpoint) (n, %, 95% CI)
- Participants with at least one solicited or unsolicited adverse reaction from respiratory tract between Day 0 and Day 28 (n, %, 95% CI)
- Participants with at least one AEFI with difficulties in breathing (asthma, spasmodic cough, pneumonia) between Day 0 and Day 28 (n, %, 95% CI)
- Participants with at least one other AEFI from the respiratory tract between Day 0 and Day 28 (n, %, 95% CI)
- Participants with at least one cough between Day 0 and Day 28 (n, %, 95% CI)
 - duration of symptoms (mean, median, SD, IQR, 95% CI)
- Participants with at least one spasmodic cough between Day 0 and Day 28 (n, %, 95% CI)
 - duration of symptoms (mean, median, SD, IQR, 95% CI)
- Participants with at least one solicited systemic adverse events between Day 0 and Day 28 (fever, headache, tiredness) (n, %, 95% CI)
- Participants with at least one unsolicited adverse event between Day 0 and Day 28 (n, %, 95% CI)

Detailed listings of individual events will be provided in an appendix of the reports.

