The results of the study showed that the frequency of symptoms in the respiratory tract and general symptoms (rhinorrhea, sneezing, nasal congestion, headache and tiredness) was high during the first two weeks, but there was no difference between the placebo group and the different dose group or the subjects colonized by the bacteria. Cough was neither more common in the high dose group nor in the subjects colonized with the vaccine strain BPZE1 as compared to the placebo group or the low and medium dose groups. No cases of cough were reported during week 3 and 4, which would have been expected if the vaccine strain BPZE1 had similarity with wild type *B. pertussis*.

This study showed that the colonization was dose-dependent - one culture positive in each of the low and medium dose group and 5 out of 12 in the high dose group. The colonization was detected between day 4 and 28 after vaccination and the time-frame was similar to that of wild-type *B. pertussis*.

All randomized subjects had detectable antibodies against at least one pertussis antigen pre-vaccination. After vaccination only the 7 subjects with culture-verified colonization of the nasopharyngeal mucosa showed increased antibody levels. The antibodies against several of the pertussis antigens appeared from day 14 or 28 and remained high during the 6 months of follow up. Thus there was a strong correlation between colonization and development of immune responses.

Interestingly, the pre-vaccination FHA, PRN and fimbriae 2/3 antibody levels were significantly higher in the culture negative subjects vaccinated with the high dose. Although the numbers were small this may explain the low frequency (5/12) of colonization. This needs to be considered in future clinical trials in child and adult populations, since very few individuals are naïve with regard to exposure to pertussis antigens either because of vaccination or infection.

The results of this study raised questions how a higher degree of colonization can be achieved for example by using a higher vaccine dose or another method for application.

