- Day 2: 2 individuals with at least 4 hours interval
- Day 3: 3 individuals with at least 2 hours interval
- Day 4: 4 individuals with at least 1 hour interval
- Day 5: 5 individuals with at least 1 hour interval

Interim safety meetings with the DSMB for recommendation to the sponsor will be held before administering the next dose. At the interim safety meetings, safety data covering 28-days of post-vaccination follow-up of group 1 and group 2, respectively, will be available. Taking into account the time for the DSMB to meet and to give its recommendations for dose escalation, group 1 volunteers will have been followed up during at least 6 weeks by the time the group 2 volunteers become vaccinated. Likewise, group 2 volunteers will have been followed up during at least 6 weeks by the time the group 3 volunteers become vaccinated.

A non-controlled group (group 4) consisting of 6 individuals will be vaccinated with 10^9 cfu of the organism (open-label) to investigate the frequency of colonization in subjects with high anti-PRN antibody levels (≥ 20 IU/ml) and PT serum IgG antibodies < 20 IU/ml.

VI.3. STUDY VISITS

This study will include 9, or if required, 10 study visits. An overview of all study visits with interviews, clinical examinations and samples to be taken are presented in I.4 "Procedural flow chart".

- Visit 1, recruitment visit 1-6 weeks before vaccination: medical history, physical examination and collection of blood and urine sample and ECG.
- Visit 2, inclusion visit, 1-6 weeks after visit 1: physical examination, collection of blood and urine (females only) sample and vaccination with vaccine or placebo.
- Visit 3, 4 ± 1 days after visit 2: physical examination, safety follow up of vaccination and collection of blood (in the high dose group 3 only) and nasopharyngeal sample.
- Visit 4, 7 ± 1 days after visit 2: physical examination, safety follow up of vaccination and collection of blood and nasopharyngeal sample.
- Visit 5, 11 ± 1 days after visit 2: physical examination, safety follow up of vaccination and nasopharyngeal sample.
- Visit 6, 14 ± 1 days after visit 2: physical examination, safety follow up of vaccination and collection of blood and nasopharyngeal sample.
- Visit 7, 21 ± 1 days after visit 2: physical examination, safety follow up of vaccination and collection of blood and nasopharyngeal sample.

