2. Confirm that a signed ICF is on file for the subject. Perform a limited physical examination and measure vital signs (oral temperature, blood pressure, heart rate and respiratory rate) and record the information in the subject's CRF.
3. Check of temporary contraindications to vaccination.
4. Collect urine sample from females and do a dip stick pregnancy testing.
5. Collect blood samples as described in section XII.3. "Blood samples". Complete the appropriate

document provided in the investigator or delegate Site file.

6. Assign the next consecutive vial number of the given dose group to the subject (refer to section VI.4. "Screening number and randomization procedure").
7. Record the allocated vial number in the participant medical record (source document).
8. Administer the study vaccine assigned to the subject by the investigator or delegate according to the randomization described in section VI.4 "Screening number and randomization procedure" and according to section X.7 "Handling and administration of study vaccine to participants".
9. Vaccination should be administered intranasally by two tuberculin syringes, one to each nostril. The fluid and the air cushion are pushed slowly out of the tuberculin syringe to ensure administration of the total volume (400 µl) into each nostril of the volunteer. In case of volunteer sneezing or blowing nose immediately after vaccination this should be recorded in the subject's CRF, but a new vaccine dose should not be given.

The staff and the volunteer should adhere to the safety instructions described in the Standard operating procedure.

10. Observe the subject for 2 hours after vaccination for immediate adverse events and record any immediate adverse event following immunization (AEFI).
11. Give the subject the Diary and an oral thermometer.
12. Inform the subject to record in the Diary.
 - a. Any respiratory tract adverse reaction (AR) occurring until Visit 8 and to specify the intensity of the reaction using definitions given in the Diary.
 - b. Any other medical event occurring until Visit 8 and to specify the intensity of the reaction using definitions given in the Diary.
 - c. The temperature as measured orally with the provided thermometer daily in the evening from day 0 until day 28. If the temperature is taken more than once during a day the highest temperature of the day should be recorded in the Diary.
 - d. Any medication taken from day 0 until Visit 8.
13. Inform the subject to

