For fever, the intensity recorded in the CRF will be the highest observed temperature of the day measured oral in degrees Celsius if temperature is taken more than once a day otherwise the evening temperature.

XIII.2. RECORDING OF SAFETY PARAMETERS

Immediate AEFI

The subjects will be under the surveillance of the investigational staff for at least 2 hours following vaccination for evaluation of immediate adverse events. The subjects have to stay at the clinic in total 6 hours after vaccination.

Adverse events (respiratory tract adverse reactions and systemic adverse events, serious or not) occurring during this time period (2 hours) will have to be reported by the investigator or delegate in accordance with applicable laws (LVFS 2011:19, Patientdatalagen 2008:355).

AEFI from the respiratory tract

AEFI with difficulties in breathing (asthma, spasmodic cough, pneumonia) will be considered as serious and reported to the DSMB and sponsor. Other AEFI from the respiratory tract will be recorded in the volunteer's CRF.

After the immediate medical surveillance at the investigator site, respiratory tract adverse events occurring from the day of vaccination (Day 0) to Day 28 following vaccination will be recorded in the Diary by the subject.

- Cough will be daily documented from Day 0 to Day 28
- Spasmodic cough, defined as rapid repetitive cough without intervening inspiration usually occurring as sudden intensified attacks of involuntary coughing (paroxysms) that may occur at different times in a way that is not regular several times per 24 hours, will be daily documented from Day 0 to Day 28
- Solicited AE from the respiratory tract that are pre-listed in the Diary will be daily documented from Day 0 to Day 28.
- Unsolicited AE from the respiratory tract will be spontaneously recorded in the Diary from Day 0 to Day 28

At Visit 8, 28 days (-1: +7) after vaccination, the Diary will have to be returned to the investigational site by the subject. The investigator or delegate will check the Diary, interview the subject and record AE from the respiratory tract in the CRF.

Systemic AEFI

After the immediate medical surveillance at the investigator site, systemic adverse events occurring from the day of vaccination (Day 0) to Day 28 following vaccination will be recorded in the Diary by the subject:

- Solicited systemic adverse events (fever, headache and tiredness) that are pre-listed in the Diary will be daily documented from Day 0 to Day 28

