- All SAE, which persist at the time of the last visit of the concerned subject (Visit 9). The investigator will inform the Data Safety Monitoring Board and INSERM of the date of resolution or stabilisation of the adverse event and will document it.
- Non-SAE assessed as possibly, probably or definitely related to the study vaccine by the investigator which persist 28 days after vaccination of the concerned subject (Visit 8)

Any SAE likely to be related to the study vaccine or to the protocol specified-intervention and occurring after subject's study termination will not be recorded into the CRF but should be reported by the investigator to the sponsor INSERM (see section 0 "*XIII.3. Reporting of Adverse Events*").

Pregnancy notification

The investigator has to notify to the sponsor, immediately and no later than 48 hours after being made aware of it, any pregnancy and its outcome, concerning the enrolled woman.

The initial report should be notified as a detailed, written report, using the CRF "Initial pregnancy notification form" and specifying estimated date of delivery, obstetrician contact and name of maternity hospital.

The investigator has to follow the subject until the end of the pregnancy or its interruption and to notify the outcome to the sponsor using the "Final pregnancy notification form".

Follow-up of pregnant participant continues until the end of the trial. Any exceptions, related to the indication of maternal treatment, should be discussed between the investigator, the coordinating investigator, the sponsor and if necessary a specialist in terato-vigilance.

Warning:

- The medical surveillance of the women and their children should be reinforced: a particular attention must be given on serious pathology occurring during pregnancy abnormalities. A SAE initial report form should be filled if any **anomaly or birth defect** is detected.

- **All voluntary interruption of pregnancy, therapeutic interruption of pregnancy or miscarriage needed a hospitalization** is considered as a SAE/SAR and should be notify as mentioned in section XIII.3. SAE reporting.

Pregnancy management:

If the investigator has been informed that a participant woman is pregnant during the study period:

- The participant must not be treated with investigational study vaccines if the pregnancy is determined before the administration.

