Qualitative variables will be described in terms of number, proportion and exact binomial confidence interval of proportion.

Intra-group comparisons will be made using McNemar test or other, depending on the number of modalities of the variables of interest.

Titers

Geometric means and their 95% confidence interval will be calculated for titers.

XV.2.2 Analysis software

Analyses will be performed using SAS® software (version 9.3 or higher) and R software.

XV.2.3 Analysis plan

A detailed statistical analysis plan will be established before the first statistical analyses of the trial.

Descriptive statistics will be provided for demographic and other baseline characteristics.

Hematology

Pre- and post-vaccination values of cell blood counts (haemoglobin, total and differential WBC, RBC and platelets) will be described for each group separately. Within group comparisons may be done using appropriate tests for paired measurements.

Primary Safety endpoint

The primary endpoint will be described per group and randomized allocation, in modified ITT population, with participants with missing follow-up data considered event-free in primary analysis. Numbers, percentages and 95% confidence intervals will be shown. Each individual component of the primary endpoint will also be described.

Secondary endpoints

Secondary endpoints will be described per group and randomized allocation, displaying numbers, percentages and 95% confidence intervals (qualitative variables); medians and interquartile intervals (quantitative variables) or geometric mean and 95% confidence interval (antibody titers).

Number, time of occurrence and duration of secondary safety endpoints will be described.

Colonization endpoints will be described (number and proportion of participants with colonization at each post-vaccination visit; number of visits during which bacteria are detected; magnitude of bacterial colonization (number of cfu) per post-vaccination visit)

Pre- and post- vaccination serum IgG and IgA antibody endpoints will be described per group and randomized allocation. Within group comparisons may be done using appropriate tests for paired measurements.

Cough, spasmodic cough and any symptom from the respiratory tract, as well as antibody titers, will be described for each of the vaccine groups and the pooled placebo group, and for the groups of colonized and non-colonized individuals.

Exploratory endpoints

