2.1.5. INTERIM REPORTING TO DSMB

Interim safety reports using descriptive statistical methods for the DSMB will be performed when all volunteers of a given group will have reached day 28, before opening enrolment to the next cohort (next higher dose).

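### The DSMB escalation report summarises cough duration by mean, SD and 95% CI around Day 28, with no rule for episodes still ongoing, so the durations are biased short

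*Combined protocol and SAP*

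**What the plan says.** SAP 3.10 lists, under cough and again under spasmodic cough, "duration of symptoms (mean, median, SD, IQR, 95% CI". SAP 2.1.5 times the report: it is prepared "when all volunteers of a given group will have reached day 28, before opening enrolment to the next cohort (next higher dose".

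The recording window is given in two ways. Protocol XIII.2 states: "Cough will be daily documented from Day 0 to Day 28", with the same window for spasmodic cough. Protocol VI.3.3, item 12, has the subject enter "Any respiratory tract adverse reaction (AR) occurring until Visit 8 and to specify the intensity of the reaction". Visit 8 may fall between Day 27 and Day 35.

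After that, Protocol XIII.2 (General requirements) has the investigator follow to resolution or stabilisation those non-serious events judged possibly, probably or definitely related "which persist 28 days after vaccination of the concerned subject (Visit 8". Note (c) of the flow chart in Protocol I.4 says the same for vaccine-related AEFI. SAEs are followed whatever their cause, and XIII.2 classes spasmodic cough as serious.

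For the final analysis, Protocol XV.2.3 says: "Number, time of occurrence and duration of secondary safety endpoints will be described". SAP 3.7, the matching SAP section, contains no duration statistic.

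No section says what happens to an episode without an end date. SAP 2.3.4 deals with partial dates and treats all types of missing value alike. SAP 2.2.1 describes available data.

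**The concern.** An episode still present when the data are cut has a known minimum length and an unknown end. A mean, SD and confidence interval treat every value as complete. Two routine ways of programming the table are open, and both err in the same direction. Cutting the episode at the last recorded day shortens it. Dropping it for lack of an end date removes the episodes most likely to be long.

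The timing makes this relevant. Protocol III.2 says of the first trial in man: "No cases of cough were reported during week 3 and 4, which would have been expected" had the vaccine strain resembled wild type. Weeks 3 and 4 are thus the period of most interest, and also the period with least room before the cut. The table goes to the board that advises whether the next dose may be given, and an error towards short durations is an error towards reassurance.

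**Working it through.** The plan states no figure for cough duration, so there is none to reproduce. Its sample-size figure, 1 − (1 − 0.126)^12 = 80.1% against the stated 80%, reproduces but concerns event counts.

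**Inputs from the documents**
- Trigger for the report: the whole group at Day 28 (SAP 2.1.5).
- Last vaccinations in a group: "Day 5: 5 individuals with at least 1 hour interval" (Protocol VI.2). If the five days are consecutive, the first vaccinees are at Day 28 + 4 = Day 32 when the last reach Day 28.
- Latest Visit 8: 28 + 7 = Day 35.
- Minimum follow-up before the next dose: 6 weeks, or Day 42 (Protocol VI.2). This is a generous cut, because the DSMB must meet before then.

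**Assumptions**
- Onset falls with equal weight on Days 15 to 28 (weeks 3 and 4).
- True durations are as shown. The documents give none.

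**If ongoing episodes are cut.** Recorded duration = min(true duration, cut − onset + 1). The mean onset day is (15 + 28)/2 = 21.5, so the mean cannot exceed cut − 21.5 + 1 = cut − 20.5.

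| Cut | Largest recordable, onset Day 15 | Largest recordable, onset Day 28 | Largest possible mean |
|---|---|---|---|
| Day 28 | 14 | 1 | 7.5 |
| Day 32 | 18 | 5 | 11.5 |
| Day 35 | 21 | 8 | 14.5 |
| Day 42 | 28 | 15 | 21.5 |

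With a Day 28 cut, true durations of 14, 21, 28, 42 and 70 days all give mean 7.5, median 7.5 and SD 4.2. With 14-day coughs, 13 of 14 onset days (93%) are cut short; with 21 days or more, all are. The table then carries almost no information about length. The median and IQR are affected as well as the mean.

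**If ongoing episodes are dropped.** Suppose half the episodes last 5 days and half 21, a true mean of (5 + 21)/2 = 13 days.
- Of the 5-day coughs, onsets on Days 15-24 finish by Day 28 (10 of 14).
- Of the 21-day coughs, none finish.
- Dropping the unfinished ones leaves only 5-day coughs: mean 5.0, SD 0.
- Cutting them instead gives (10 × 5 + 4 + 3 + 2 + 1)/14 = 4.29 for the short coughs and 7.5 for the long, so (4.29 + 7.5)/2 = 5.9 days.

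Both are well below 13, and they differ from each other because the SAP does not choose.

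**The case against.** A reader might infer that a pertussis-like cough would be recorded as lasting about a week however long it lasted. The documents do not support that.
- Follow-up does not simply stop at Day 28. Related events are followed until they resolve or stabilise, and the threshold for a possible relation (Protocol XIII.1) is low. Spasmodic cough falls under SAE follow-up regardless of causality. Visit 9, and Visit 8' where held, ask again about respiratory reactions.
- A hard Day 28 cut is not established. The diary may run to Visit 8, and the earliest vaccinees will be past Day 28.
- The 7.5 days is an average over 1 to 14 days under the strictest cut, not a value that any given cough would take.

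Nor would the DSMB depend on this table to notice such an event. Spasmodic cough, being classed as serious, prompts an ad-hoc meeting (Protocol XIII.7). Clinical whooping cough is itself a stopping consideration, with no duration threshold. The primary endpoint counts cough of grade 2 or higher whatever its length. SAP 3.10 also supplies listings of individual events, which are readable with 16 people per group.

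All of this stands, and it limits the consequence. It does not repair the table: later follow-up cannot supply an end date that does not exist when the report is written. The listings are also not required to mark an episode as ongoing. It is fair to add that SAP 3.10 is silent rather than prescribing truncation. The bias arises under either of the obvious readings, but the text does not mandate one.

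**Conclusion.** The point holds for the interim duration table. SAP 3.10 applies complete-data statistics to right-censored durations, and the result is biased short whenever an episode is ongoing at the cut. For onsets in weeks 3 and 4 the ceiling on the mean is 7.5 days at a Day 28 cut, 14.5 at Day 35 and 21.5 at Day 42. These figures rest on evenly spread onsets and on the cut chosen. They illustrate the ceiling and do not predict what the trial will show.

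The primary endpoint and the event counts are untouched. In the final data the end date is at risk only for non-spasmodic cough judged unrelated, and the Visit 9 interview may recover some of those. It would be wrong to conclude that the DSMB would miss a pertussis-like illness. The supportable conclusion is that one safety summary used for dose escalation errs towards reassurance and is cheap to correct.

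**What to change.** In SAP 3.10, and wherever duration is described under Protocol XV.2.3:
1. Define the source of the end date, and use the latest known end date where follow-up past Day 28 exists.
2. Flag each episode ongoing at the data cut, in the table and in the listing, and report the number ongoing.
3. Replace the mean, SD and 95% CI with a Kaplan-Meier median where estimable. Otherwise give the range, with ongoing episodes shown as at least x days.
4. Reconcile Protocol VI.3.3 (diary until Visit 8) with XIII.2 (daily recording to Day 28), so that the last recordable day is the same throughout.

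The cost is a few lines of SAP text and one extra column. The Kaplan-Meier median may be inestimable with one or two episodes, or when most are ongoing; the at-least-x-days form then serves. Kaplan-Meier also assumes that duration is unrelated to the time left before the cut. If late-onset coughs are the long ones, that fails, so the number ongoing should be shown in every case.
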